9.10.3.1. Tumor Response by Tumor Volume Score (TVS)

In addition to being assessed using RECIST v1.1 (primary endpoint), tumor response will also be assessed using TVS. Objective response rate by TVS is defined as the proportion of participants with a CR or PR.

Tumor volume score ORR at Week 25 will be compared between the 2 treatment groups using the same approach used for the primary endpoint analysis. The tumor response status at Week 25 based on TVS will follow the same approach described in Table 2 for the primary endpoint.

Sensitivity analyses similar to the ones planned for the primary endpoint will be performed.

A forest plot summarizing the difference in TVS ORR at Week 25 between vimseltinib and placebo and its associated Wald 95% CI will be generated for the subgroups listed in Section 9.10.5 to evaluate the consistency of treatment effects in the subgroups.

All TVS data will be presented in by-participant listings.

9.10.3.2. Range of Motion (ROM)

Measurement of the affected and contralateral, non-affected joint will be assessed using a goniometer. The measurement (in degrees) of the affected joint will be used to derive a relative ROM obtained through normalization to the measurement from a reference standard value provided by the American Medical Association per motion and type (active or passive).

At screening, the motion with the smallest relative ROM value (worst) will be identified, and this motion will be used for evaluating the change in relative ROM subsequently. Only the motion with the most impaired ROM at screening will be selected for subsequent analyses. If there are ties, the multiple motions with the same relative ROM value at screening will be identified, and the average of relative ROM values will be calculated at each post screening visit and be used in the analysis as the single relative ROM value for that specific visit.

The main analysis of relative ROM will be based on the active measurement relative to a reference standard and will consist in a comparison between treatment groups of the mean change from baseline at Week 25 using a MMRM. The different timepoints that will be included in the model are Weeks 13 and 25, which respectively correspond to Day 1 of Cycles 4 and 7. The observed value and change from baseline in relative ROM will be summarized with descriptive statistics by timepoint and treatment group. The mean change from baseline will be calculated and presented in figure format at each timepoint by treatment group. In addition, such mean changes may be displayed by joint type and/or motion.

A forest plot summarizing the 95% CI of the difference in mean of change from baseline at Week 25 between vimseltinib and placebo without adjusting for the stratification factors will be generated for the subgroups listed in Section 9.10.5 to evaluate the consistency of treatment effects in the subgroups.

Additional analyses of these data will be performed on results based on the passive measurement and results normalized to the measurement obtained from the contralateral, non-affected joint.

All ROM data will be presented in by-participant listings.

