9.10.3. Key Secondary Endpoints

As specified in the following sub-sections, multiple secondary endpoints will be analyzed using a mixed model for repeated measurements (MMRM) using the sandwich estimator to estimate the variance-covariance matrix. The dependent variable will be the change from baseline. Each of these models will include fixed effects for treatment group, timepoint, treatment group by timepoint interaction, stratification factor for region (U.S. versus non-U.S.), stratification factor for tumor location (lower limb vs. all other), and the baseline value of the corresponding endpoint. Statistical comparisons between treatment groups will be made at the specified timepoint. For the analysis of ROM only, tumor location will be replaced with joint type (knee, ankle, or other). An unstructured variance-covariance matrix will be used. If the unstructured variance-covariance matrix fails to converge, then alternative structures will be utilized. Statistical comparisons between treatment groups will be made based on a contrast statement at Week 25.

Analyses of the secondary endpoints described in the following sub-sections will be limited to data from Part 1 and will focus on comparisons between participants who received vimseltinib versus participants who received placebo during this period. The exception to this rule is for duration of response presented in Section 9.10.4.3.

These analyses may also be performed on the PP Set if the proportion of participants from the ITT Set who are excluded from PP Set exceeds 5%.

A separate analysis plan will describe the process for identifying the minimally clinical important difference (MCID) for PROMIS-PF, Worst Stiffness, and ROM. A responder analysis for each of these endpoints based on the MCID of each endpoint as determined by the analysis will be performed.

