Х	X	Does your health now limit you in doing heavy work around the house like scrubbing floors, or lifting or moving heavy furniture?
X	X	Does your health now limit you in lifting or carrying groceries?
Х	Х	Does your health now limit you in doing moderate work around the house like vacuuming, sweeping floors or carrying in groceries?
X	X	Does your health now limit you in going OUTSIDE the home, for example to shop or visit a doctor's office?
X		Does your health now limit you in bending, kneeling, or stooping?

The observed value and change from baseline in PROMIS-PF T-score will be summarized with descriptive statistics by timepoint and treatment group. The mean change from baseline will be calculated and presented in figure format at each timepoint by treatment group.

A forest plot summarizing the 95% CI of the difference in mean of change from baseline at Week 25 between vimseltinib and placebo without adjusting for the stratification factors will be generated for the subgroups listed in Section 9.10.5 to evaluate the consistency of treatment effects in the subgroups.

All PROMIS-PF data will be presented in by-participant listings.

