9.10.5. Sub-group Analyses

The primary efficacy endpoint and key secondary efficacy endpoints will be analyzed in participant subgroups defined as follows:

• Tumor location (lower limb vs all other)

- Region (U.S. vs non-U.S.)
- Participants with disease located in large joints (shoulder, elbow, hip, or knee) vs small joints (joints other than the shoulder, elbow, hip, or knee)
- Participants with disease located in the knee
- Disease subtype (localized vs diffuse)
- Participants at sites in the EU region only
- Age $(18 \le age < 50, 50 \le age < 65, age \ge 65)$
- Gender (female vs male)
- Prior surgery (yes vs no)
- Prior imatinib/nilotinib (yes vs no)

The applicable key secondary efficacy endpoints are TVS, ROM, PROMIS-PF, worst stiffness NRS, EQ-VAS and BPI-30 response.

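### The subgroup forest plots for ROM, PROMIS-PF, worst stiffness and EQ-VAS name no model and, read plainly, drop the baseline covariate; keeping it would usually sharpen the subgroup estimates at almost no cost

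*SAP*

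**What the plan says.** SAP 9.10.3 sets one main model for the four continuous key secondary endpoints, an MMRM on change from baseline: "Each of these models will include fixed effects for treatment group, timepoint, treatment group by timepoint interaction", then region, "stratification factor for tumor location (lower limb vs. all other), and the baseline value of the corresponding endpoint". For ROM, joint type takes the place of tumor location.

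The subgroup plots are described separately, in the same terms, in SAP 9.10.3.2 (ROM), 9.10.3.3 (PROMIS-PF), 9.10.3.4 (worst stiffness) and 9.10.3.5 (EQ-VAS). Each plot shows the 95% CI of "the difference in mean of change from baseline at Week 25 between vimseltinib and placebo without adjusting for the stratification factors". Its stated purpose is "to evaluate the consistency of treatment effects in the subgroups".

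SAP 9.10.5 adds only the list: "The primary efficacy endpoint and key secondary efficacy endpoints will be analyzed in participant subgroups defined as follows". Ten subgroup factors follow, without a model, a minimum level size or an interaction test. Protocol 12.4.9 likewise lists subgroups without a method.

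**The concern.** A forest plot of this kind is read against the overall result. The overall result is adjusted for baseline. The subgroup rows are described as a difference in mean change, with no model and no mention of baseline. If baseline is dropped, two things follow within a level. A chance difference between the arms in starting value passes into the estimated difference in change, and the interval is usually wider than one that uses the baseline value already collected.

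The effect is largest in small levels. About 40 participants are planned on placebo (SAP 5). If a level held 25% of them (an assumption), it would have about 10, or 8 to 9 after the planned 15% dropout. At that size, noise from baseline can make subgroups look different when they are not, or hide a real difference.

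**Working it through.** **Inputs from the documents.** About 80 vimseltinib and 40 placebo participants, 2:1, with 15% dropout (SAP 5). The main model has baseline as a covariate (SAP 9.10.3). The plots are unadjusted for the stratification factors (SAP 9.10.3.2 to 9.10.3.5).

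**Inputs assumed.** The correlation r between baseline and Week 25 is not given; the range used is 0.3 to 0.9. Subgroup sizes are not given; 2:1 levels from 40 vs 20 down to 8 vs 4 are used. Variance is taken as equal at baseline and Week 25.

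**The plan's own figure.** The only sizing figure is 98% power for the primary endpoint. It reproduces (98.3% by exact enumeration of Fisher's test at 80 vs 40, 35% vs 5%) but does not bear on this point.

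**Step 1: large-sample precision.** In units of the single-visit variance, the variance of raw change is 2(1 − r), and the residual variance after baseline adjustment is 1 − r². The ratio of interval widths, adjusted to raw, is √[(1 − r²) / (2(1 − r))] = √[(1 + r)/2].

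- r = 0.3: √0.65 = 0.806, about 19% narrower
- r = 0.5: √0.75 = 0.866, about 13% narrower
- r = 0.7: √0.85 = 0.922, about 8% narrower
- r = 0.9: √0.95 = 0.975, about 2.5% narrower

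**Step 2: small levels.** The large-sample ratio ignores the lost degree of freedom and chance correlation between arm and baseline. Simulation (4,000 data sets per cell, t intervals) gives these mean width ratios for adjustment by baseline only, against raw change:

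| Level (vimseltinib vs placebo) | r = 0.3 | r = 0.5 | r = 0.7 | r = 0.9 |
|---|---|---|---|---|
| 40 vs 20 | 0.81 | 0.88 | 0.93 | 0.98 |
| 20 vs 10 | 0.82 | 0.89 | 0.94 | 0.99 |
| 12 vs 6 | 0.84 | 0.90 | 0.96 | 1.01 |
| 8 vs 4 | 0.86 | 0.93 | 0.99 | 1.04 |

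Up to r = 0.7, baseline adjustment does not widen the interval on average, even at 8 vs 4. At r = 0.9 there is no useful gain, and a slight loss in the smallest levels.

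**Step 3: adding the stratification factors back.** With baseline plus two factors that have no effect on outcome, the ratios at r = 0.3/0.5/0.7/0.9 are 0.86/0.92/0.98/1.04 at 20 vs 10, 0.91/0.98/1.05/1.10 at 12 vs 6, and 1.02/1.09/1.16/1.23 at 8 vs 4. Omitting those factors in small levels is therefore reasonable.

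**Step 4: chance imbalance.** The standard error of the baseline difference between arms, in baseline SDs, is √(1/n₁ + 1/n₂). A baseline imbalance moves the raw difference in change by −(1 − r) times its size. At 10 vs 5 the standard error is √(1/10 + 1/5) = 0.548. At r = 0.5, a one-standard-error imbalance moves the estimate by 0.5 × 0.548 = 0.274 SD.

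This is not a second harm on top of step 1. At r = 0.5 the raw standard error is 0.548 and the adjusted one is 0.866 × 0.548 = 0.474, and 0.474² + 0.274² = 0.548². The shift is exactly the extra variance that makes the raw interval wider.

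**The case against.** The strongest objection is that the text excludes only the stratification factors. It does not say that baseline or the repeated-measures model is dropped. SAP 9.10.3.2 describes the main MMRM contrast itself as a comparison of mean change at Week 25, so similar words could mean an MMRM here too. A raw difference adjusts for nothing, so the qualifier would also be redundant. This stands as far as it goes: loss of the baseline term is inferred. But the SAP names the MMRM for each main analysis and for none of these plots, so the raw difference remains the more natural reading. If baseline is in fact kept, the losses above do not arise and the remedy is the same sentence of clarification.

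A reader might go further in four ways that the documents do not support.

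- *The subgroup estimates are biased.* Under randomization the imbalance has mean zero, and the unadjusted interval already allows for it.
- *Leaving out the stratification factors is itself an error.* A factor is constant within its own subgroup levels, cells elsewhere may be sparse, and step 3 shows that adding factors can widen small-level intervals. SAP 9.10.3.6 also uses an unstratified interval for BPI-30.
- *The full MMRM should be refitted in every level.* The PRO models have six visits, hence 6 × 7/2 = 21 unstructured covariance parameters, with a sandwich estimator. SAP 9.10.3 already provides for non-convergence in the whole set. Switching to a simpler model only for small levels would mix estimators within one plot.
- *Many levels will have only a handful of placebo participants.* The documents give no subgroup distribution, so this can only be assumed.

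**Conclusion.** The point holds in a limited form. The four plot descriptions name no model and, on their plain reading, discard a baseline value that the main analysis uses. Subgroup estimates would then be noisier than they need to be at low to moderate correlation: large-sample intervals would be about 19%, 13% or 8% narrower with adjustment at r = 0.3, 0.5 or 0.7. The benefit shrinks in very small levels and all but disappears near 0.9. It would therefore be wrong to infer that the planned intervals are always wider than necessary.

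The size rests on an assumed correlation, assumed level sizes, equal variances at the two visits, and the inference that baseline is dropped. The stakes are modest. The plots are descriptive and lie outside the testing hierarchy in SAP 9.10.1, so no primary or key secondary conclusion depends on them.

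**What to change.** In SAP 9.10.3.2, 9.10.3.3, 9.10.3.4 and 9.10.3.5, state that the subgroup difference at Week 25 and its 95% CI are estimated with adjustment for the baseline value of the endpoint. An example is ANCOVA of change at Week 25 on treatment and baseline within each level. Apply the same model to every row of the plot and keep the stratification factors out. For ROM this also settles whether joint type, which is not a randomization factor, enters the subgroup estimate: under this wording it does not.

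The cost is one sentence in four places and a simple model. Adjustment uses one degree of freedom per level, and intervals may be slightly wider in very small levels if the correlation is high (4% at 8 vs 4 with r = 0.9). A Week 25 ANCOVA also still uses only participants observed at Week 25, so the plots will not match the MMRM in its use of earlier visits. That is acceptable for a descriptive display, provided that it is stated.

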9.10.3.3. Physical Function

The main analysis of PROMIS-PF will consist of a comparison between treatment groups of the mean change from baseline at Week 25 using a MMRM. The different timepoints that will be included in the model are Weeks 5, 9, 13, 17, 21, 25 which respectively correspond to Day 1 of Cycles 2, 3, 4, 5, 6, and 7. Values for analysis will be the earliest collected value in each cycle.

Fifteen questions from the PROMIS-PF item bank will be asked regardless of tumor location for the individual participant. The questions use one of two 5-point verbal rating scales: either 1 = "unable to do", 2 = "with much difficulty", 3 = "with some difficulty", 4 = "with a little difficulty", and 5 = "without any difficulty"; or 1 = "cannot do", 2 = "quite a lot", 3 = "somewhat", 4 = "very little", and 5 = "not at all." There is no specified recall period. The subset of questions used for scoring is based on the location of the tumor (upper or lower body) based on Gelhorn et al (6). The PROMIS-PF is scored using the Assessment Center API using the table below to generate a T-score which is used for analysis where "x" denotes the question is utilized for scoring. The T-score rescales the raw sum score into a standardized score with mean of 50 and a SD of 10 based on the US general population. If a participant answers at least half of the questions for their tumor location, then the T-score generated based on the API

scoring manual will be used for analysis and those questions with missing responses are ignored for scoring. If a participant answers less than half of the questions for their tumor location, then the T-score will be calculated and presented in listings but will not be used for analysis.

Table 3: PROMIS Scoring Based on Tumor Location

Lower	Upper	Question
X	x	Are you able to push open a heavy door?
X	X	Are you able to exercise for an hour?
X	X	Are you able to carry a heavy object (over 10 pounds/5kgs)?
X	X	Are you able to dress yourself, including tying shoelaces and buttoning your clothes?
X	X	Are you able to carry a laundry basket up a flight of stairs?
X		Are you able to stand for one hour?
X		Are you able to go up and down stairs at a normal pace?
X		Are you able to go for a walk for at least 15 minutes?
	X	Are you able to lift 10 pounds (5kg) above your shoulder?
	X	Are you able to change a light bulb overhead?
Х	X	Does your health now limit you in doing heavy work around the house like scrubbing floors, or lifting or moving heavy furniture?
X	X	Does your health now limit you in lifting or carrying groceries?
Х	Х	Does your health now limit you in doing moderate work around the house like vacuuming, sweeping floors or carrying in groceries?
X	X	Does your health now limit you in going OUTSIDE the home, for example to shop or visit a doctor's office?
X		Does your health now limit you in bending, kneeling, or stooping?

The observed value and change from baseline in PROMIS-PF T-score will be summarized with descriptive statistics by timepoint and treatment group. The mean change from baseline will be calculated and presented in figure format at each timepoint by treatment group.

A forest plot summarizing the 95% CI of the difference in mean of change from baseline at Week 25 between vimseltinib and placebo without adjusting for the stratification factors will be generated for the subgroups listed in Section 9.10.5 to evaluate the consistency of treatment effects in the subgroups.

All PROMIS-PF data will be presented in by-participant listings.

9.10.3.4. Worst Stiffness Numeric Rating Scale (NRS)

The main analysis of worst stiffness NRS will consist of a comparison between treatment groups of the mean change from baseline at Week 25 using a MMRM. The different timepoints that will be included in the model are Weeks 5, 9, 13, 17, 21, 25 which respectively correspond to Day 1 of Cycles 2, 3, 4, 5, 6, and 7. For each of these timepoints, the value used for analysis will be the average of the results obtained at weeks 2 and 3 of the previous cycle. For example, the value used for a participant at Week 25 (Cycle 7 Day 1) will be the average of the observations collected during the 2nd and 3rd week of Cycle 6. At least 4 measurements are required to compute this average, otherwise it is set to missing.

The observed value and change from baseline in worst stiffness NRS will be summarized with descriptive statistics by timepoint and treatment group. The mean change from baseline will be calculated and presented in figure format at each timepoint by treatment group.

A forest plot summarizing the 95% CI of the difference in mean of change from baseline at Week 25 between vimseltinib and placebo without adjusting for the stratification factors will be generated for the subgroups listed in Section 9.10.5 to evaluate the consistency of treatment effects in the subgroups.

All worst stiffness NRS data will be presented in by-participant listings.

9.10.3.5. EQ-5D-5L

The main analysis of the EQ-VAS will consist of a comparison between treatment groups of the mean change from baseline at Week 25 using a MMRM. The different timepoints that will be included in the model are Weeks 5, 9, 13, 17, 21, 25 which respectively correspond to Day 1 of Cycles 2, 3, 4, 5, 6, and 7. Values for analysis will be the earliest collected value in each cycle.

The observed value and change from baseline in EQ-VAS will be summarized with descriptive statistics by timepoint and treatment group. The mean change from baseline will be calculated and presented in figure format at each timepoint by treatment group.

A forest plot summarizing the 95% CI of the difference in mean of change from baseline at Week 25 between vimseltinib and placebo without adjusting for the stratification factors will be generated for the subgroups listed in Section 9.10.5 to evaluate the consistency of treatment effects in the subgroups. The EQ-5D-5L will be summarized by frequency and percentage for each level of each dimension by timepoint and treatment group.

All EQ-5D-5L data will be presented in by-participant listings.

9.10.3.6. Brief Pain Inventory – Response

A responder analysis based on the BPI worst pain NRS item and analgesic use will be performed. A responder will be defined as a participant who: (i) experienced a decrease of at least 30% in the mean BPI worst pain NRS item and (ii) did not experience a 30% or greater increase in narcotic analgesic use. The change in BPI worst pain NRS for responder assessment will be assessed by comparing data collected during a 14-day period prior to the current visit with baseline values collected prior to the first dose of study drug. This will be referenced as BPI-30 response. A value for BPI worst pain NRS will be computed for each participant at Day 1 of individual cycles. This value will be the average of the measurements obtained during weeks 2 and 3 of the previous cycle. At least 4 measurements are required during weeks 2 and 3 of the previous cycle to compute this average, otherwise it is set to missing. If it is set to missing, BPI-30 response for that cycle will be assigned as a non-response. For derivation of BPI-30 response, the narcotic analgesic use will be evaluated for periods corresponding to the BPI worst pain NRS assessment periods. For participants who use different types of narcotic analgesic and/or dosage levels, analgesic use will be calculated by converting equianalgesic dosing to morphineequivalent doses as described in Table 4 (3, 4, 5). A sensitivity analysis which defines a responder as experienced a decrease of at least 30% in the mean BPI worst pain NRS item and no increase in narcotic analgesic use.

Table 4: Narcotic Analgesic Drug (NAD) conversions to morphine-equivalent dose

Narcotic Analgesic Drug	Conversion Factor
Buprenorphine (SL)	80
Buprenorphine (TD)	100
Codeine	0.1
Dihydrocodeine	0.1
Fentanyl patch	100
Fentanyl (SL)	0.125
Hydrocodone	0.67
Hydromorphone	4
Levorphanol	11
Methadone	
1-20 mg/day	4
21-40 mg/day	8
41-60 mg/day	10
≥61-80 mg/day	12
Meperidine hel	0.1
Morphine	1
Oxycodone	1.5
Oxymorphone	3
Pethidine	0.125
Pentazocine	0.37
Propoxyphene	0.23
Tapentadol	0.33
Tramadol	0.1

Conversion factors were sourced from WHO guidelines (4) when available and next from CDC guidelines (3). In cases where neither WHO nor CDC guidelines provided a morphine-equivalent conversion factor, alternate guideline such as CONSORT (5) were used.

BPI-30 response at Week 25 will be compared between the 2 treatment groups using the same approach used for the primary endpoint analysis. A summary of narcotic use over time will be provided.

A forest plot summarizing the unstratified 95% CI of the difference in BPI response rate at Week 25 between vimseltinib and placebo will be generated for the subgroups listed in Section 9.10.5 to evaluate the consistency of treatment effects in the subgroups.

All BPI data will be presented in by-participant listings.

